8.1.10 Delivery of the intervention and follow-up

The champions will raise awareness of the HWS intervention throughout the study duration through a communication plan developed with the support of the advisor and LEO's OH team.

As described in section X above, all study participants in the intervention SMEs will receive the full intervention, while control SMEs will receive a health and wellbeing status report followed by a work and health training post intervention for individuals nominated by the SME.

At intervention sites, once participants are consented into the study the champion will support the intervention roll-out ensuring all employees within their participating SME are aware of, supported and encouraged to access the HWS offered by the LEO. Participants within SMEs who have not consented into the study will still be able to engage with the intervention, and will be invited to consent into the follow-up surveys (at 6 and 12 months) instead. To optimise the value of the study and uptake of components of the intervention, practical actions to overcome challenges will be taken where appropriate.

9 Phase 3: Evaluation

9.1 Work Package 3: Quantitative evaluation and social return on investment analysis (Leads: AM/EW)

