Control arm SMEs will not receive the intervention. All SMEs including those in the control arm will however receive summary data reports. To limit any contamination effects, this report will be provided after the employee survey outcome data collection at baseline and 12 months. These reports offer insights into the workforce's health and wellbeing, along with recommendations for independent, future action on employee health and wellbeing. This approach has been successfully applied in the NIHR funded IGLOO study to secure engagement from control organisations. Control SMEs will also be invited to nominate an

employee for work and health training post-intervention to transfer new knowledge and skills into the control SMEs. Together, these services would otherwise cost at least £5,000 per SME, representing an attractive financial offer to control SMEs.

iv) Study outcomes

The intervention seeks to deliver HWS within SMEs, aiming to foster healthier employees and workplaces, with a primary focus on evaluating work engagement. Three main reasons underpin this decision: first, evidence demonstrating correlation between work engagement and a broad range of health and work outcomes, including physical and mental health outcomes [15], performance and absenteeism [16], job commitment and satisfaction [17], and unemployment and disability pension uptake [18]; second, many companies routinely track work engagement, and have strong incentives to do so accurately, as a key performance indicator, making it a practical and accepted measure, as evidenced by the NHS [19]; third, our previous research identified its relevance, especially in SME contexts, where openness to health conversations is low and research engagement is challenging.

Secondary outcomes have been informed by workplace health evidence and following feedback from our ESPG, alongside our experience of working with SMEs in the Midlands Engine Mental Health Productivity Pilot (MHPP), a programme to support mental wellbeing in the workplace. These will include mental wellbeing, health behaviours, safety behaviours, job satisfaction, productivity, and cost.

v) Logic model Groundwork from the Development Award provided sufficient evidence to underpin the logic model illustrating how the intervention is expected to work, as follows:

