7.1.5 Recruiting participating SMEs and randomisation of sites to control or intervention group

The three participating LEOs will each help us to recruit between six and eight SMEs seeking to improve their HWS provision in their supply chain to participate in the study. We will aim for eight SMEs per LEO, but acknowledge we may have difficulty recruiting the full complement across all supply chains. If it not deemed feasible to recruit eight SMEs in an LEO, we will accept a minimum of six SMEs, which should still allow for adequate power for our study (see Section 8.1.6 – Power calculation). A maximum four-month window period will be used to identify and recruit the 18-24 SMEs (six to eight SMEs from each of LEO supply chain) into the study during the pre-randomisation stage. Those who are interested will be told to contact the research team. We will set up a meeting with each interested SME to ensure that they are eligible for the study, to explain the study to them and answer any questions they may have, and to share a provisional version of the study contracts with them. If all are satisfactory and the SME consents to participate in the study, the study team will collect data about the workforce demography and size of each SME.

In late November/early December 2025, randomisation will occur (assigning SMEs to intervention or control arm). We would ideally randomise all eight SMEs per LEO together, however, we will conduct the first randomisation in each LEO at this time if a minimum of four SMEs have been recruited. We will then begin to roll-out the study in these randomised SMEs, and continue to recruit additional companies in background, which we can then randomise at a later point and who would have a slightly delayed beginning for the study/HWS intervention. Therefore, randomisation may occur at six separate time periods (twice for each LEO), ensuring there are no delays in the randomisation and delivery of the intervention from each LEO. There will be no more than a month or two between the staggered beginning of the study roll-out in SMEs within each LEO. We will endeavour to recruit even numbers of SMEs for each LEO to ensure that half of all participating sites are in the intervention arm and half are in the control arm. Randomisation will be undertaken by a co-investigator who is not involved in recruiting or working directly with the SMEs (likely [name] - University of Leeds).

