8.1.3 Control arm (Comparator)

Control arm SMEs will not receive the intervention. However, in order to provide some form of compensation and incentive to take part in the study, control arm SMEs will receive the same summary data reports following data collection, and champion training post-study evaluations, that are also provided to the intervention group SMEs. These reports offer insights into the workforce's health and wellbeing, along with recommendations for independent, future action on employee health and wellbeing. To limit the risk that employee outcome survey responses are influenced by these summary data reports (contamination

[figure not shown]
effects), they will be provided to control arm SMEs after the employee survey has been conducted at each time point (baseline, 6, 12 and 18 months). This approach has been successfully applied in the NIHR-funded IGLOO study to secure engagement from control organisations. Additionally, once all study data has been gathered, control SMEs will also be invited to nominate an employee for work and health training to transfer new knowledge and skills into the control SMEs.

Together, these services would otherwise cost at least £5,000 per SME, representing an attractive financial offer to control SMEs.

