Personal identifiable data will be stored on the REDCap software for the duration of the study and personal identifiable data will only be accessible for members of the study team based at Guy's and St Thomas NHS Foundation Trust. However, all downloaded data files from REDCap will have personal identifiable data removed at the point of data extraction and at this point the data file will then become fully pseudonymised and kept in a secure, password file, and only accessible by the study team responsible for conducting the study. Additionally, the separate personal data extracted at the time of download will be removed

from the main data file, along with information on the specific reasons why they provided their contact information (i.e. to be entered into the prize draw, to hear about the study results). Included in this contact information data file will be each participant's unique study ID, and this will be used to link participants' contact information back to their response. This will mean that the survey will be pseudonymized for the duration of data analysis and storage. If it is necessary to email data files among research team members, this will be done by sending securely via email in encrypted and password protected data files. Passwords will be sent to the recipient in a separate email.

Paper-based questionnaires returned to the central study team will be manually entered into the database (REDCap software) by the study team member. To securely return completed questionnaires, participants who choose to complete a paper survey will be provided with a pre-paid business reply envelope marked 'Confidential'. Upon receipt by the research team, paper-questionnaires will be processed in a timely manner.

Participants will be informed in the PIS that they can withdraw from the study at any point during the study period (up to 31 March 2027) without giving a reason. For participants completing the survey online, they can close the browser before submitting their answers at any point, if they wish to discontinue. Those completing a paper survey will be able to destroy the survey themselves or submit the incomplete survey to the research team. Incomplete surveys which are returned to the research team, either via secured post for paper surveys or submitted on REDCap for online surveys, will be included in the analysis.

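### What control SMEs receive before the 18-month survey, and when participants may withdraw, are not stated consistently with the 18-month follow-up

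*Protocol*

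**What the plan says.** **Training of control SMEs.** Three places describe it.

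- Section 3 (engaging control arm SMEs) invites each control SME to nominate an "employee for work and health training post-intervention to transfer new knowledge and skills into the control SMEs".
- Section 8.1.10 says the status report is "followed by a work and health training post intervention for individuals nominated by the SME". The sentence refers back to an earlier section whose number was never filled in.
- Section 8.1.3 fixes the timing twice: "champion training post-study evaluations", and then "once all study data has been gathered, control SMEs will also be invited to nominate an employee for work and health training".

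Section 8.1.2 sets delivery at 12 months. Section 6.1 puts the end of the intervention period at 12 months and a further survey 6 months later. Section 9.3 analyses the change from baseline to 18 months, between arms, as the long-term intervention effect.

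**Summary reports.** Section 3 says "this report will be provided after the employee survey outcome data collection at baseline and 12 months". Section 8.1.3 says "they will be provided to control arm SMEs after the employee survey has been conducted at each time point" and lists baseline, 6, 12 and 18 months.

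**Withdrawal.** Section 9.1.2 says the PIS will tell participants they can "withdraw from the study at any point during the study period (up to 31 March 2027". Section 12.2 repeats the date with the word approximately. Section 21 gives the study end date as 30 November 2027. On the start, section 7.1.5 says "In late November/early December 2025, randomisation will occur", with a second batch in each LEO starting at most a month or two later.

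**The concern.** The training is not neutral for the comparison. Section 8.1.3 calls it champion training, and trained champions are a core part of the intervention arm. Section 3 gives its purpose as moving knowledge and skills into the control SMEs. If it took place between months 12 and 18, the comparator for the long-term effect would no longer be untreated. Sites working from different sections could also do different things. Section 8.1.10 is the delivery section, so it is one that people running the study would plausibly follow.

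The report schedules cannot both be followed. The reports carry recommendations for action, and section 8.1.3 itself treats them as a possible source of contamination, so their timing should be fixed.

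The withdrawal date is information for participants. Someone asked to complete the 18-month survey would have been told of a withdrawal window that had closed before that survey opened.

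**Working it through.** **1. Training: the passages side by side**

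| Section | Timing given | Allowed in months 12 to 18? |
|---|---|---|
| 3 | after the intervention, no month | yes, on a literal reading |
| 8.1.10 | after the intervention, no month, unfilled cross-reference | yes, on a literal reading |
| 8.1.3 | after all study data are gathered | no |

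Delivery ends at month 12 and the last survey is at month 18, so the literal reading opens a window of 18 − 12 = 6 months. It could apply to any of the 9 to 12 control SMEs. Training after month 18 is also after the intervention, so the three texts can be reconciled. Sections 3 and 8.1.10 are looser than 8.1.3; they do not strictly contradict it.

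**2. Reports: the passages side by side**

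Section 3 gives two releases (after baseline and 12 months). Section 8.1.3 gives four (after baseline, 6, 12 and 18 months). The releases after 6 and 18 months appear in one section and not the other.

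**3. Withdrawal date: calendar check**

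Inputs: randomisation in late November or early December 2025 and a stagger of 0 to 2 months (section 7.1.5); follow-up of 18 months (section 6.1); withdrawal limit 31 March 2027 (sections 9.1.2 and 12.2); end date 30 November 2027 (section 21).

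Assumptions: late November is taken as 20 November and early December as 10 December. Baseline is taken at randomisation. That is the earliest case, because section 7.1.5 places inception meetings and data-collection arrangements after allocation.

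Survey date = randomisation + stagger + months of follow-up.

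| Start | Month 12 | Month 18 |
|---|---|---|
| 20 Nov 2025 | 20 Nov 2026 | 20 May 2027 |
| 10 Dec 2025 | 10 Dec 2026 | 10 Jun 2027 |
| 10 Feb 2026 (2-month stagger) | 10 Feb 2027 | 10 Aug 2027 |

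- Gap from 31 March 2027 to the earliest 18-month survey: 50 days. To the latest in the table: 132 days. That is about 2 to 4 months.
- Reverse check: 31 March 2027 minus 18 months is 30 September 2025, before any randomisation. The stated date therefore cannot be reproduced from the 18-month schedule. It lies only about 16 months after the first randomisation.
- 31 March 2027 does fall after every 12-month survey in the table.
- 30 November 2027 falls 112 to 194 days (about 4 to 6 months) after the 18-month surveys. It covers them for any baseline up to 30 May 2026.

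Two other texts also fit a shorter follow-up: section 8.1.10 invites later consenters to surveys at 6 and 12 months only, and section 9.1.3 lists data at three time points against four in section 9.3. One explanation is that some text was not updated for the 18-month wave; that is an inference.

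**The case against.** The strongest reply is that section 8.1.3 governs. It is the section devoted to the control arm, it states the timing twice, and it protects the 18-month contrast. Section 3 is introductory, and section 8.1.10 presents itself as a summary of something already described. This largely stands. A reader might infer that the 18-month contrast is unprotected, or that the protocol schedules training at month 12. It does neither: no passage names month 12, and the most specific passage excludes it.

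A reader might also want to put a size on the dilution. The protocol gives no basis for one. Control SMEs nominate an employee, whereas intervention SMEs get a 12-month multi-component package with manager training, at least two champions and advisor support. Any fraction of the planned effect assigned to the training alone would be invented.

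On the reports, section 8.1.3 gives both arms the same reports and releases them after each survey to limit contamination. They are also part of the incentive for control SMEs. Holding back the recommendations until the last survey would be a debatable trade-off, and the inconsistency does not require it. What remains is that two schedules are stated.

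On the date, a reader might infer that the study closes before its last survey. It does not, because section 21 runs to 30 November 2027. Section 12.2 also says approximately, and makes completed analysis the point after which data cannot be withdrawn. But a gap of 2 to 4 months is more than approximately can absorb, and section 9.1.2 gives the date without that qualifier.

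**Conclusion.** Three inconsistencies stand, and they should be corrected.

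- **Training:** an ambiguity. Sections 3 and 8.1.10 leave open a 6-month window that section 8.1.3 closes. Harm is conditional: a site would have to train early and the training would have to work. The long-term contrast would then be pulled towards no difference by an unknown amount. The 12-month contrast is unaffected by this wording.
- **Reports:** a direct conflict, two releases against four.
- **Withdrawal date:** a wrong figure on the protocol's own calendar, about 2 to 4 months before any 18-month survey. This rests on baseline being no earlier than randomisation; a later start widens the gap. It is an error in participant information and does not affect the validity of the 18-month comparison.

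**What to change.** 1. Reword sections 3 and 8.1.10 to match section 8.1.3, so that no control SME is trained before its 18-month survey has closed. Fill in the missing section number in 8.1.10.
2. State one report schedule, the same in both arms, and use it in sections 3 and 8.1.3.
3. Replace 31 March 2027 in sections 9.1.2 and 12.2 and in the PIS with a date after the last 18-month survey and before data analysis is completed. On the calendar above, the date must be later than about 10 August 2027, or later still if roll-out starts after randomisation.
4. In the same edit, bring the survey list in section 8.1.10 and the number of time points in section 9.1.3 into line with section 9.3.

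The cost is a text amendment and a revised PIS. Design, sample size and data collection do not change, and control SMEs wait no longer for training than section 8.1.3 already requires.

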8.1.4 Masking & other measures taken to avoid bias

As referred to above, upon consenting into the study, SMEs will be randomly allocated to intervention or control arms by a member of the research team who has had no prior interaction with the employees at any SME. Prior to randomisation, we will match SMEs within each LEO by workforce size (i.e., the companies with the two highest workforce sizes will be matched, then with the 3rd and 4th highest workforce size will be matched, and so on). SMEs within each of these pairings will then be randomised. This will help us to ensure that our intervention and control arms are balanced for size, considering some SMEs may have 200+ employees while others may have 10-20. Due to the nature of the intervention, it is not possible to blind participants in the LEOs and SMEs to their group allocation. Companies will be informed of the allocation soon after consenting for their involvement in the study prior to consent.

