8.1.5 STUDY FLOW DIAGRAM (INTERVENTION and CONTROL ARM)

8.1.6 Participant Selection

Participants recruited into the study will be drawn from the 18-24 SMEs recruited to take part in the study and we will work with the local collaborator at each SME to develop an acceptable method to invite participants to take part. We will monitor recruitment from each participating centre and will relay information back to the local sites, so they are aware of the recruitment uptake.

Sample size calculation and justification

A previous study of a workplace intervention to build and sustain work engagement [27] suggests a mean (SD) work engagement score of 5.08 (1.40) in the control and 5.76 (0.86) in the intervention group. As the proposed intervention is SME-based, sample size calculations must account for clustering effects. With the rho of 0.1 and the above values for expected change in work engagement scores, seven SMEs per intervention arm ensure 90% power at a 5% significance level (2-sided) to detect differences in the primary outcome. To account for participant attrition, we plan to over-sample with nine to twelve SMEs per arm, depending on the availability of interested SMEs, and to maximise the recruited employee sample per SME.

Given the workforce size of SMEs (between 10 and 249 employees), and assuming a uniform response rate across the recruited SMEs no greater than 50%, the anticipated number of participating employees per SME will range from 5 to 125, equivalent to an average of 65 employees per SME. Put together, the anticipated sample size across the minimum of 18 recruited SMEs would be 1170 employees, rising to 1560 employees if we can recruit the full complement of 24 SMEs. This ensures robustness in detecting meaningful changes in work engagement attributable to the proposed intervention.

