Questionnaire responses will be converted into relevant outcome metrics (e.g. work engagement score, health economic utility scores). Employee-level outcome data collected at baseline, 6 months, 12 month and 18 months will be analysed using two-level multilevel regression models, with employee participants nested within SMEs. Analyses will include an interaction term between the intervention group and time period, to assess differences in change in work engagement (and then separately for each of the secondary outcome measures) between baseline, 6-months (work engagement only) and 12 months (i.e. short-term intervention effect), and between baseline and 18 months (long-term intervention effect) between the intervention and the control SMEs.

Further analyses will assess effect modification by organisational (information collected at the recruitment process like workforce size, sector, relative size of customer, and length of business operation) and intervention delivery factors (dependent on the variation in the recruited SMEs), including a multiplicative interaction between intervention group and each of the factor under consideration. If there is evidence of significant effect modification, we will stratify our analyses accordingly to determine the strength and the direction of the effect by levels of the modification factor.

Economic evaluation will take the form of a cost-consequence analysis (whereby disaggregated non-monetised changes in outcomes are presented alongside costs to inform decision making) and a Social Return on Investment (SROI) [24,25], whereby benefits observed after 12 and 18 months are monetised using published sources, and potential longer-term impacts are explored using different assumptions about the sustainability of changes in behaviour and health. Resources used in intervention delivery will be assessed using data collected in WP2 and costed using a micro-costing approach [26]. Resources used by companies and employees will be assessed using questionnaire data (example measures listed above in WP1), and costs incurred will be calculated using relevant unit cost data. Differences in the results will also be presented in terms of the person- and SME-level moderators defined above and the perspective of the analysis, which will include the employer, employee and wider economy perspectives.

Engagement activity log

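### Late survey entry is written for intervention SMEs only, and the analysis does not require a baseline, so the group-by-time contrast can pick up a change in who responds

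*Protocol*

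**What the plan says.** **Entry rule (Protocol 8.1.10).** The paragraph opens with "At intervention sites, once participants are consented into the study the champion will support the intervention roll-out". The champion is to make sure that all employees of the SME, not only those who consented, are "aware of, supported and encouraged to access the HWS offered by the LEO". Employees who have not consented may nevertheless "engage with the intervention, and will be invited to consent into the follow-up surveys (at 6 and 12 months) instead". No corresponding late invitation for control SMEs appears in this section or elsewhere in the protocol.

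**Analysis (Protocol 9.3).** "Employee-level outcome data collected at baseline, 6 months, 12 month and 18 months will be analysed". The data "will be analysed using two-level multilevel regression models, with employee participants nested within SMEs". The effect is read from the interaction: "Analyses will include an interaction term between the intervention group and time period, to assess differences in change in work engagement". Nothing here makes a baseline response a condition of entering the model.

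**Blinding (Protocol 8.1.4).** "it is not possible to blind participants in the LEOs and SMEs to their group allocation".

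**Planning values (Protocol 8.1.6).** Work engagement is taken as "5.08 (1.40) in the control and 5.76 (0.86) in the intervention group", with an intracluster correlation of 0.1, a response of at most 50% and an average of 65 participating employees per SME. Seven SMEs per arm are said to give 90% power, and nine to twelve per arm are planned.

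**The concern.** A difference in change from baseline isolates the intervention effect only if the people behind the follow-up mean are comparable with those behind the baseline mean, or if any change in composition is the same in both arms. The late-entry rule weakens both conditions.

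Late joiners have no baseline value. They enter after randomisation, know their arm, and may already have used the services. The model as described would place them in the 6- and 12-month intervention means and leave them out of the baseline mean. If control SMEs recruit no late joiners, or recruit them differently, the shift in respondents does not cancel between arms.

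The outcome affected is work engagement, the primary outcome. The pool of possible late joiners is not small: with a response of at most 50%, those who did not take part at baseline are at least as many as those who did.

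**Working it through.** **1. The plan's own figure.** Inputs are from Protocol 8.1.6.
- Difference: 5.76 − 5.08 = 0.68.
- Root-mean-square SD: √[(1.40² + 0.86²)/2] = 1.162.
- Unclustered n per arm for 90% power, two-sided 5%: 2 × [1.162 × (1.96 + 1.2816)/0.68]² = 61.3.
- Design effect: 1 + (65 − 1) × 0.1 = 7.4.
- SMEs per arm: 61.3 × 7.4/65 = 6.98, so 7.

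The stated sample size reproduces and is not in question. The same inputs supply the standard errors below.

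**2. Standard error of the arm contrast**, SE = SD × √[2 × 7.4/(k × 65)]:
- k = 9 SMEs per arm: 0.185.
- k = 12: 0.160.

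This is the cluster-adjusted SE of a between-arm difference at one wave, as the sample size uses. The SE of the interaction also depends on correlations over time that the protocol does not give.

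**3. Form of the bias.** Let q be the late joiners' share of intervention follow-up respondents, and g their mean difference from the baseline cohort when there is no intervention effect. With no matching entry in controls, the intervention arm's change from baseline is shifted by q × g. Adding SMEs does not shrink this.

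**4. Illustration.** Both q and g are assumptions; the protocol gives neither.
- g = half an SD = 1.162/2 = 0.58, in either direction.
- q = 20%: for example, 50% consent at baseline, a quarter of the rest join later and all of the baseline cohort is retained: 0.125/(0.5 + 0.125) = 0.20.
- q = 30%: for example, 30% of the rest join later and 70% of the baseline cohort is retained: 0.15/(0.35 + 0.15) = 0.30.

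Two-sided type I error = Φ(−1.96 − b/SE) + 1 − Φ(1.96 − b/SE), where b is the bias:

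| q | bias b | share of 0.68 | 9 SMEs per arm | 12 SMEs per arm |
|---|---|---|---|---|
| 20% | ±0.12 | 17% | 10.0% | 11.6% |
| 30% | ±0.17 | 26% | 15.1% | 18.6% |

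The error rates use b rounded to two decimals. Unrounded (0.116 and 0.174), they are 9.6% and 15.6% at nine SMEs per arm, and 11.2% and 19.3% at twelve. The sign of g does not change them.

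**5. Wider range (also assumed).** Take 50% consent at baseline, 10–50% of the rest joining later, and 70–100% retention of the baseline cohort. Then q runs from 9% to 42%.
- g = 0.34: bias 0.03–0.14 points, type I error 5.3–14%.
- g = 0.68: bias 0.06–0.28 points, type I error 6.3–43%.

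At the low end the effect is negligible.

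**6. Precision lost by leaving late joiners out.** The variance of an SME mean is proportional to 0.1 + 0.9/m. Suppose late joiners make up 20–30% of 65 respondents, so m falls to 52 or 45.5. The factor goes from 0.1138 to 0.1173 or 0.1198, and the SE rises by √(0.1173/0.1138) − 1 = 1.5% or √(0.1198/0.1138) − 1 = 2.6%.

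**The case against.** **Entry in one arm only.** A reader might infer that late joiners can enter only in intervention SMEs. The protocol does not say so. It is silent on controls, all employees of participating SMEs are eligible (8.1.7), and nothing bars late consent in a control SME. What stands is that the invitation is written in a paragraph about intervention sites, with no counterpart for controls.

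**Bias in favour of the intervention.** A reader might also infer that late joiners are satisfied users who raise the intervention mean. The documents do not support a direction. Satisfied users would bias upward; employees who stayed out at baseline because they were less engaged would bias downward. Nor have these people necessarily refused: not having consented also covers those who never responded.

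**A matter for the statistical analysis plan.** Analysis sets are commonly defined there, and that plan is not shown. It could restrict the primary analysis to baseline responders. Section 9.3 neither admits nor excludes people without a baseline in so many words; their inclusion follows from analysing all collected data. This objection carries weight for the analysis set but not for the entry rule, which is protocol content: no later plan can recover control employees who were never invited.

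**A workforce-level design is legitimate.** The study is implemented at organisational level, and surveying the current workforce at each wave is defensible. That needs the same entry rule in both arms, which is the point at issue. It is also fair to say that a baseline cohort is not free of selection: SMEs learn their allocation early, and champions help distribute invitations at intervention sites (8.1.9).

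**Conclusion.** The point holds as a gap in the entry rule combined with an analysis description that does not exclude its consequences. Followed as written, sections 8.1.10 and 9.3 allow employees with no baseline, recruited after randomisation and possibly after exposure, into the follow-up intervention means with no stated counterpart in controls. The primary contrast can then reflect who responds as well as what the intervention does.

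The size is unknown. Under the assumed 20–30% share and half-SD gap, the bias is 0.12–0.17 points in either direction, against a planned difference of 0.68. Type I error is then about 10–15% at nine SMEs per arm and 12–19% at twelve. These error rates rest on the assumed share and gap, a normal approximation, and the between-arm SE implied by the plan's own inputs. With few late joiners or a small gap the problem is negligible. It should be fixed; confidence is moderate.

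**What to change.** - **Section 8.1.10:** state that any late invitation is made identically, and at the same times, in intervention and control SMEs. This has to be in place before the 6-month survey, because missed control invitations cannot be made good afterwards.
- **Section 9.3:** state that the primary analysis of work engagement uses employees who consented and completed the baseline survey, in both arms. Late joiners' data go only into an all-respondent sensitivity analysis and the process evaluation.

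**Cost.** A sentence in each section, plus the extra invitations in control SMEs. Late joiners' data leave the primary analysis, with an SE increase of about 1.5–2.6% in the illustration, because the number of SMEs dominates precision. The primary result then describes the baseline cohort rather than the whole current workforce. The change does not remove selection at baseline consent or differential attrition.
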